4.5.3 Completers Analysis Set

The completers population will consist of all subjects who received both study treatments and completed both treatment periods in the study. The completers population will be used in the sensitivity efficacy analyses.

4.5.4 Per Protocol Set

Per Protocol Set (PAS) will consist of all subjects in the completers analysis sets which did not experience any protocol deviations affecting study primary analyses.

4.6 Demographics and Baseline Characteristics

Demographic variables include:

- Birth Year
- Age in Years (as derived in CRF)
- Gender (and, if female the childbearing potential status)
- Race
- Ethnicity

Demographic variables will be listed by subject as defined in SAP section 4.2.4.

Demographic summaries will be based upon the Safety Set as defined in Section 4.5.

Continuous variable of age in years and categorical demographic variables (Gender, Race and Ethnicity) will be summarized descriptively based on Safety analysis set as defined in SAP section 4.2.5.

4.7 DLco

By subject listings of DLco data will be provided as defined in SAP section 4.2.4.

DLco data will be summarized at screening as defined in SAP section 4.2.5.

4.8 Medical History and Concomitant Illnesses

Medical history is assessed at screening and include prior and ongoing medical illnesses and conditions and prior surgical procedures not related to the primary diagnosis.

Medical history summaries will be based upon the Safety Set as defined in Section 4.5.

| Trevi Therapeutics, Inc. | | | |
|--------------------------|-------|------|---------------------------|
| TR12 | | | Statistical Analysis Plan |
| | •11 1 | 11 . | |

Medical History terms will be coded using Medical Dictionary for Regulatory Activities (MedDRA) version 22.0 or later version.

Medical History terms will be listed by subject.

4.9 **Prior and Concomitant Medications**

Any medication taken by a subject within the 14 days prior to the screening period, and during the course of the study, will be recorded on the eCRF along with the reason for use. During the study, each subject will be instructed to report the use of all medication, including over-the-counter (OTC) medications, herbal medications, vitamins, and nutritional supplements on the study specific medication log. After screening, prohibited or restricted medications are to be recorded on the corresponding Concomitant Medication eCRF.

Medications will be coded using the World Health Organization Drug Dictionary (WHODD), version global 2019 March B3 or later version and will be presented by Reported Term, WHODD Anatomical-Therapeutic-Chemical (ATC) therapeutic class IV and preferred term (PT).

- Medication start and stop dates will be compared to the dates of IMP intake in both Treatment Periods 1 and 2: Medications that start and stop prior to the date of first of IMP intake in Treatment Period 1 will be classified as prior;
- A therapy is concomitant to the NAL-ER if it started before the date of first NAL-ER intake and stopped on or after the date of first NAL-ER intake or if it started on or after the date of first NAL-ER intake and before the date of last NAL-ER intake.

A therapy is concomitant to the placebo if it started before the date of first placebo intake and stopped on or after the date of first placebo intake or if it started on or after the date of first NAL-ER intake and before the date of last placebo intake.If medication start and/or stop dates are missing or partial, the dates will be compared as far as possible with the date of first dose of study medication.

Prior and concomitant medications will be listed by subject as defined in SAP section 4.2.4.

Concomitant medications summaries will be based upon the Safety Set as defined in Section 4.5.

Concomitant medications will be tabulated by Anatomical and Therapeutic Class (ATC) of World Health Organization (WHO) drug and preferred term, and as defined in SAP section 4.2.5. Of note: some medications may be concomitant to both treatment arms; these will be duplicated in the corresponding summary table.

Subgroup of patients with prior and concomitant use of anti-fibrotic therapies will be identified based on the review od study medical monitor. Efficacy summaries may be presented in the subgroup of patients with anti-fibrotic therapies as described in the relevant sections of this SAP.

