The primary efficacy endpoint of percent change in daytime cough frequency (coughs per hour) will be analyzed using a mixed-effects model with sequence, treatment, and time (Day 22) as fixed effects, the baseline value as a covariate, site as a random effect, and subject as a random repeated effect. There will be no imputation for dropouts or missing data for assessments not completed at study visits. A log transformation will be applied to daytime cough frequency; in the presentation of results, log-scale fitted mean treatment group differences at Day 22 will be back-transformed to fitted ratios of geometric means.

As a sensitivity analysis, a negative binomial model will be fitted with the number of coughs at Day 22 as the outcome, with terms for sequence, treatment, and time, as well as baseline cough frequency and subject, and duration of daytime (in hours) as an offset. An autoregressive covariance structure will be assumed for study visits, and the site random effect will use an unstructured covariance matrix.

Secondary efficacy endpoints will be summarized using descriptive statistics. For continuous endpoints (e.g., change from baseline), summaries will include mean, median, standard deviation, minimum, and maximum. For discrete variables (e.g., frequency), summaries will include number of instances and percentage of total instances for that category or time period.

Safety

Name of Sponsor/Company:	Name of Product:	Name of Active Ingredient:
Trevi Therapeutics, Inc.	Nalbuphine Extended-Release	Nalbuphine HCl
	Tablets	

The incidence of adverse events will be summarized through the presentation of proportions by Medical Dictionary for Regulatory Activities (MedDRA) body system classification and preferred term. Vital signs and laboratory data will be summarized using descriptive statistics. The extent and duration of use of prohibited or restricted medications will be similarly summarized using descriptive statistics. No formal statistical analysis will be performed on safety outcomes; inferences, if any, will be derived through clinical review and interpretation.

Adverse events of special interest (AESI) that code to the most relevant abuse-related MedDRA preferred terms will be tabulated and descriptive narratives will be written. Additional adverse events that are considered "possibly related to abuse potential" will be tabulated separately.

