6.5 Safety Monitoring

An independent Data Safety Monitoring Board (DSMB) will periodically review safety data. The frequency of data review and DSMB processes are outlined in the DSMB charter.
Subjects will be closely monitored for safety. AEs will be continuously evaluated throughout the study. Vital signs, locally reviewed and central cardiac core laboratory-read ECGs, physical examinations, spirometry, clinical laboratory testing will be conducted to monitor subject safety.

Although nalbuphine is not a controlled substance in the US or the UK, AEs of special interest (AESIs) that code to the most relevant abuse-related Medical Dictionary for Regulatory Activities (MedDRA) preferred terms will be tabulated and descriptive narratives will be written. Additional AEs that are considered "possibly related to abuse potential" will be tabulated separately (the *FDA's "Assessment of Abuse Potential of Drugs: Guidance for Industry" [2017]*). The list of MedDRA preferred terms for AESIs will be described in the statistical analysis plan (SAP).

Subjects will complete the SOWS on a daily basis for 14 days following the last dose of investigational product. Any subjects who are prematurely discontinued from investigational product will also complete the SOWS daily for the 14 days following the last dose of investigational product (unless consent is withdrawn). The SOWS is a self-administered scale for grading opioid withdrawal symptoms and will be collected via the study issued e-diary.

If subjects experience significant withdrawal symptoms during the 2-week safety observation period, they should contact the Investigator. At the Investigator's discretion, they will be offered treatment.

The most frequently reported AEs from NAL ER Phase 1 and 2 clinical studies were primarily in the nervous system and GI organ system categories, consistent with other opiates. The specific AEs that are considered to be expected with use of NAL ER are nausea, vomiting, somnolence, sedation, dizziness, vertigo, and constipation. These are generally mild or moderate in severity and usually resolve over the titration and early dosing period.

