11.6 Concomitant Medications

Concomitant medications will be tabulated by Anatomical and Therapeutic Class (ATC) of World Health Organization (WHO) drug, preferred term, and treatment group. A medication's usage will be considered concomitant if it was started or continued after administration of the study medication.

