4.12.1.2 Definition of Treatment Emergent Adverse Event (TEAE)

A TEAE is an AE occurring on or after the initial administration of investigational product. In this study, AEs may be treatment emergent with respect to treatment assumed in treatment period 1 or treatment period 2. The following will apply:

- AEs with onset date prior to the date of first of IMP intake in Treatment Period 1 will be considered as AEs non treatment emergent.
- AEs with onset date on or after the date of first IMP intake in Treatment Period 1 (but before first IMP intake in Treatment Period 2) will be considered as Treatment Period 1 TEAE.
- AEs with onset date on or after the date of first IMP intake in Treatment Period 2 will be considered as Treatment Period 2 TEAE.

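### SAP 4.9 leaves medications started on the last NAL ER dosing day or in the washout after NAL ER out of the NAL ER column, although adverse events on those same days are attributed to NAL ER

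*SAP*

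**What the plan says.** SAP 4.9 (Prior and Concomitant Medications) gives two ways for a drug to count under NAL ER. The carry-in clause takes a drug that "started before the date of first NAL-ER intake and stopped on or after the date of first NAL-ER intake". The new-start clause takes one that "started on or after the date of first NAL-ER intake and before the date of last NAL-ER intake". The placebo rule has the same two parts, but its new-start clause applies "if it started on or after the date of first NAL-ER intake and before the date of last placebo intake", so it opens on a NAL ER date. SAP 4.2.5 puts concomitant medications, like other safety data, under the treatment actually received.

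Three other places bear on this:

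- Protocol 11.6: "A medication's usage will be considered concomitant if it was started or continued after administration of the study medication". No closing date is given.
- SAP 4.12.1.2: an event from first Period 1 intake onward "but before first IMP intake in Treatment Period 2) will be considered as Treatment Period 1 TEAE". Period 2 events run from first Period 2 intake with no stated end, and SAP 3.2.3.1 collects events through the Period 2 follow-up visit.
- Protocol 6.5, on significant withdrawal symptoms in the two weeks off drug: "At the Investigator's discretion, they will be offered treatment".

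The Statistical Methods part of the protocol synopsis also promises: "The extent and duration of use of prohibited or restricted medications will be similarly summarized using descriptive statistics". SAP 4.9 says only that such drugs are recorded on the eCRF, and plans a general tabulation by ATC class and preferred term.

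**The concern.** The medication table and the adverse event table are both read by treatment received, but for NAL ER they cover different days. An event on the last dosing day or in the following washout enters the NAL ER column, while a drug started that day to treat it does not.

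Safety and tolerability is a primary objective (Protocol 5.1). Protocol 6.6 acknowledges physical dependence as a class concern and builds in the two-week observation period for that reason. The excluded days are therefore the days on which treatment for withdrawal could begin, together with the day on which a subject stops dosing. For subjects who stop early the new-start window shrinks with the last-dose date. For a subject dosed on a single day it is empty, although that subject is in the Safety Set.

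SAP section 1 undertakes to record departures from the protocol in the section on changes, now 4.15. That section mentions neither the closing date nor the missing summary of prohibited or restricted medication.

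**Working it through.** The plan states no figure to reproduce; the check is date logic.

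**Inputs.** First dose Day 1 and last dose the morning of Day 22 (Protocol Table 1, notes 3 and 4). Follow-up *g* = 14 ± 2 days after last dose (note 2), so 12, 14 or 16. Period 2 baseline is taken to fall on the same day as Visit 6, the usual case under Protocol 6.3.1, with Period 2 Day 1 on the next day. The subject is assumed to complete each period on schedule.

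**Step 1: can the carry-in clause rescue a late start?** No. It requires a start before first NAL ER intake, so a drug begun on Day 22 or later fails it however long it is taken.

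**Step 2: compare the windows, counting days from first NAL ER intake.**

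- TEAE window = 22 + *g* days.
- New-start window = 22 − 1 = 21 days, because the upper limit is strict.
- Gap = (22 + *g*) − 21 = *g* + 1 days.

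| *g* | TEAE window | New-start window | Starts not counted under NAL ER | Share of days |
|---|---|---|---|---|
| 12 | Days 1–34 (34) | Days 1–21 (21) | Days 22–34 (13) | 13/34 = 38% |
| 14 | Days 1–36 (36) | Days 1–21 (21) | Days 22–36 (15) | 15/36 = 42% |
| 16 | Days 1–38 (38) | Days 1–21 (21) | Days 22–38 (17) | 17/38 = 45% |

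**Step 3: where do these drugs go?** Take *g* = 14 and count calendar days from Period 1 Day 1. Visit 6 is day 22 + 14 = 36, Period 2 Day 1 is day 37, last Period 2 dose is day 37 + 21 = 58, and Visit 10 is day 58 + 14 = 72.

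- *Arm 1 (NAL ER days 1–22, placebo days 37–58).* The placebo new-start clause as written is 1 ≤ start < 58. All uncounted NAL ER starts, days 22–36, satisfy it and go under placebo, even if the drug was taken for one day in the washout. A subject who never takes placebo has no last placebo date, so the drug falls under neither treatment.
- *Arm 2 (placebo days 1–22, NAL ER days 37–58).* The uncounted starts are days 58–72, again 15 days. The placebo new-start clause would need start ≥ 37 and start < 22, which no date satisfies. Placebo carry-in needs a start before day 1. These drugs fall under neither treatment.

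**Step 4: would a one-word change be enough?** Replacing before with on or before adds Day 22 (22 days covered) and still leaves out the 14 washout days.

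**The case against.** The strongest reply is that a drug first started after dosing has ended is not taken together with that treatment, and that it is a common convention to class it as post-treatment. Protocol 11.6 has no rule for assigning drugs to treatments in a crossover, so the SAP had to supply one, and a medication window need not match the adverse event window. On this view the only clear slip is the loss of the last-dose day.

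Part of this stands: a separate post-treatment category would be defensible. But SAP 4.9 sets up no such category. It sends the drugs to placebo in Arm 1 and to no column in Arm 2, and no convention supports either result.

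A reader might infer that withdrawal or its treatment would be hidden. The documents do not support that. All medications are listed by subject with treatment and relative study day (SAP 4.9, 4.2.4). Adverse event listings show other actions taken, and AESIs, which include withdrawal complaints (Protocol 10.2.3), are listed separately (SAP 4.12.1.8). SOWS is summarized by treatment and study day (SAP 4.12.10). Treatment of withdrawal is also at the Investigator's discretion, so how often it would occur is unknown.

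A reader might also take 42% as the share of medications lost. It is a share of calendar days. Protocol 6.5 expects side effects mainly during titration and early dosing, and 9.6.3 allows anti-emetics to be prescribed at baseline, so starts need not be spread evenly.

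On prohibited medication, the promise stands in the synopsis but not in Protocol 11.6 or 11.8, so the protocol is itself uneven. The general ATC table would still show opioids or CNS depressants started under NAL ER before the last-dose date.

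**Conclusion.** The point holds as a classification error in the concomitant medication summary table. On the protocol calendar, 15 of 36 start days (13 of 34 to 17 of 38) are never counted under NAL ER in either sequence. In Arm 1 subjects who go on to placebo, those starts are credited to placebo, which for these drugs shifts the comparison away from NAL ER. In Arm 2 they are credited to neither treatment. The net effect on the whole table cannot be stated, because the placebo clause also copies Arm 1 starts on NAL ER into the placebo column and captures no new starts in Arm 2.

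The day counts assume a period completed on schedule and Visit 6 serving as Period 2 baseline. Washout here means the washout after NAL ER. It would be wrong to infer that every washout start is missed: in Arm 2, a drug begun in the washout after placebo and still taken at first NAL ER intake counts under NAL ER by carry-in.

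No efficacy, power or alpha figure is affected. The correction should be made, but the trial's conclusions on efficacy do not depend on it.

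**What to change.** In SAP 4.9:

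1. Include starts on the date of last intake of each treatment.
2. Attribute drugs started after last dose to the treatment just stopped, up to the day before first intake of the next period, or through Visit 10 after Period 2. Show each once under that treatment, in a separate row for drugs started after last dose, and not also among the on-treatment rows. A drug still being taken at first intake of the next treatment also meets that treatment's carry-in clause; SAP 4.9 already provides for a drug appearing under both.
3. Open the placebo new-start clause at first placebo intake. Without this, changing the end dates alone leaves the comparison distorted.
4. Either add the summary of extent and duration of prohibited or restricted medication by treatment that the protocol synopsis promises, or declare its omission in SAP 4.15. Declare there any remaining departure from Protocol 11.6.

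The cost is one revised derivation, an extra row, and at most one added table. Start and stop dates and prohibited-medication records are already on the eCRF, so no data collection changes.

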BMI = body mass index; PK = pharmacokinetic; AE = adverse event; conmeds = concomitant medications

- = Investigational product administration in each treatment period will be separated by a washout interval of 2 weeks between dosing.
- 2 = Follow-up will occur 14±2 days after the last administration of investigational product.
- 3 = First dose of investigational product for Treatment Period 1 is taken the evening of Day 1 after removal of the cough monitor.
- 4 = Last dose of investigational product for Treatment Period 1 is the morning dose of Day 22.
- 5 = Electrocardiogram (ECG) to be recorded prior to blood sampling when possible at scheduled visits where PK and/or clinical labs are obtained. Subjects should be in the supine position for at least 5 minutes prior to obtaining ECGs with all 3 tracings captured within a 3-5 minute window.
- 6 = Includes heart rate, blood pressure, respiratory rate, body temperature, and pulse oximetry. Vital signs should be taken prior to blood sampling and measured after the subject has been seated for at least 5 minutes.
- 7 = Performance of spirometry should adhere to ATS/ERS guidelines; required as part of meeting inclusion criterion #2.
- 8 = A negative urine pregnancy test will be confirmed prior to randomizing any female subjects of childbearing potential.
- 9 = Blood and urine samples for clinical laboratory testing should be obtained after 8 hours of fasting whenever possible. Clinical chemistry, hematology, urinalysis, and coagulation will be assessed.
- 10 = Baseline values for the purposes of the statistical analysis of treatment effect on daytime cough frequency during that crossover period. First dose of investigational product on Treatment Day 1 will be taken after removal of the cough monitor.
- 11 = Monitor will be placed on the subject by site staff at the end of the visit.
- 12 = Digital cough monitor hookup (24-hour recording); monitor will be worn until the evening of the following day in order to obtain at least a full 24-hour recording period of cough frequency. At the end of each recording session, the monitor will be removed at home by the subject prior to bedtime. On Treatment Day 1, the monitor will be removed prior to taking the first dose of investigational product. Subject to be provided with appropriate shipping material to return monitor for downloading of cough data (after removal).
- 13 = Administered on paper for screening; required as part of meeting inclusion criterion #6.

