4.2.1 Treatment Period, Treatment and Sequence

In this Study, two treatment periods are planned: Treatment Period 1 includes visits from Screening (day -45 to -2) to Visit 6 follow-up (day 36); Treatment Period 2 include visits from Visit 6 Baseline (day -1) to Visit 10 follow-up (day 36).

Two treatments are planned for administration to each subject: NAL ER tablets and Placebo tablets.

Two sequences (arms) are also planned; subjects in sequence 1 will receive active NAL ER tablets followed by crossover Placebo tablets in Treatment Period 2; subjects in sequence 2 will receive Placebo tablets followed by crossover NAL ER tablets in Treatment Period 2.

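### SAP 4.9 opens the window for new medication on placebo at first NAL ER intake, so the placebo column of the concomitant-medication table is wrong in both arms

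*SAP*

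**What the plan says.** SAP Section 4.9 classifies each medication by comparing its dates with the dates of study drug intake. A drug is prior under this rule: "Medications that start and stop prior to the date of first of IMP intake in Treatment Period 1 will be classified as prior".

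Each treatment then has a rule with two limbs. The first covers drugs carried in from before that treatment, the second covers drugs newly started.

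- NAL ER, second limb: "if it started on or after the date of first NAL-ER intake and before the date of last NAL-ER intake".
- Placebo, first limb: "it started before the date of first placebo intake and stopped on or after the date of first placebo intake".
- Placebo, second limb: "if it started on or after the date of first NAL-ER intake and before the date of last placebo intake".

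Section 4.9 adds that "some medications may be concomitant to both treatment arms; these will be duplicated in the corresponding summary table". Section 4.2.5 includes concomitant medications among the tables presented by treatment actually received, whichever period it was received in.

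The order of treatments is set in SAP Section 4.2.1: "subjects in sequence 1 will receive active NAL ER tablets followed by crossover Placebo tablets in Treatment Period 2", and "subjects in sequence 2 will receive Placebo tablets followed by crossover NAL ER tablets in Treatment Period 2". Nothing elsewhere in the SAP or protocol corrects the placebo rule. Protocol Section 11.6 gives only a general definition, under which a drug started or continued after study medication is concomitant.

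**The concern.** The four limbs should use the dates of their own treatment. Three do. The second placebo limb opens at a NAL ER date and closes at a placebo date, and in a crossover the order of those two dates depends on the arm. In one arm the window is too wide, in the other it cannot be satisfied.

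Safety and tolerability is a primary objective, and this table sets NAL ER beside placebo. Protocol Section 9.6.3 expects nausea, headache and dizziness at initiation and titration, and permits anti-emetics and other symptomatic treatment. Short courses begun after the first dose are the entries the rule misplaces. In Arm 1 the error adds NAL ER-period drugs to the placebo column and so hides a difference. In Arm 2 it removes placebo-period drugs and so exaggerates one. Nothing makes the two errors cancel.

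**Working it through.** There is no plan figure to reproduce; the check applies the rule as written to the planned dates.

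**Timeline in study days, counted from the first dose of Period 1**
- Period 1 dosing: days 1 to 22. Protocol Section 6.2: "Last dose of investigational product for Treatment Period 1 is the morning dose of Day 22".
- First washout: days 23 to 36. The Day 36 follow-up visit is normally also Day -1 of Period 2 (Protocol Section 6.3).
- Period 2 dosing: days 37 to 58 (37 + 21 = 58). Final follow-up: day 72 (37 + 35 = 72).

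**Second placebo limb as written:** first NAL ER day ≤ start < last placebo day.
- Arm 1 (NAL ER days 1–22, placebo days 37–58): 1 ≤ start < 58. This takes in the whole NAL ER period and the first washout.
- Arm 2 (placebo days 1–22, NAL ER days 37–58): 37 ≤ start < 22. This is empty. With the ±2-day visit window, first NAL ER intake falls on days 35 to 39, always after day 22, so it stays empty.

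The first placebo limb cannot recover the Arm 2 drugs, because it requires a start before first placebo intake.

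**Counting every whole-day start/stop pair.** Period starts run over the 21 days before the last dose day, since the rules require a start before that date.
- Start and stop within one treatment period: 22 + 21 + … + 2 = 252.
- Start and stop within the first washout: 14 × 15 / 2 = 105.
- Start in Period 1, stop any time to day 72: sum of (73 − s) for s = 1 to 21 = 21 × 73 − 231 = 1302.
- Of these, still in use on day 37 or later: 21 × 36 = 756. Stopped before day 37: 1302 − 756 = 546.

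| Date pairs | Counted under placebo, as written | With first placebo intake |
|---|---|---|
| Arm 1, start and stop in NAL ER period | 252 of 252 | 0 of 252 |
| Arm 1, start and stop in first washout | 105 of 105 | 0 of 105 |
| Arm 1, start in NAL ER period, stop any time | 1302 of 1302 | 756 of 1302 |
| Arm 2, start in placebo period, stop any time | 0 of 1302 | 1302 of 1302 |

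In the third row, the 756 pairs still running at first placebo intake belong under placebo by the first limb; the other 546 are wrongly there.

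In Arm 2, the 756 pairs that run on to first NAL ER intake are counted under NAL ER only. The remaining 546, including all 252 that start and stop within the placebo period, fall under neither treatment and are not prior either. That conflicts with Protocol Section 11.6. For an Arm 2 subject who never takes NAL ER, the opening date of the window does not exist.

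These are counts of possible date pairs that show the logic, not forecasts of how many medications are affected.

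**The case against.** The strongest reply is that this is an evident copying slip in a descriptive table. The NAL ER rule shows the intent, SAP Section 4.2.5 states that tables follow treatment received, Section 4.1 provides for independent checking of outputs, and the by-subject listings keep every drug. Concomitant medication is not among the listed safety assessments, no test is planned on it, and tolerability events are captured as treatment-emergent adverse events under a separate, consistent period rule (SAP Section 4.12.1.2).

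Much of this stands as a limit on the size of the problem. The NAL ER column is right. Drugs already in use before first placebo intake are classified correctly in both arms. The anti-fibrotic subgroup is identified by medical monitor review, so it does not depend on this rule. The documents cannot show whether the slip reached the code.

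It does not remove the problem. The SAP is the programming specification, and code checked against it would reproduce the error. The note that drugs concomitant to both treatments appear twice is correct in itself, but it would make the false Arm 1 duplicates look intended. Correct listings do not make the by-treatment table correct.

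A further objection is that drugs confined to the first washout would fit neither treatment after the correction. That is true, but it is a separate gap which already exists in Arm 2 under the current wording.

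**Conclusion.** The rule is wrong as written and should be corrected. Followed literally, it gives a wrong placebo column in both arms. Arm 1, about half the subjects under 1:1 randomisation, contributes all its new NAL ER-period drugs and washout drugs to placebo, including those stopped before any placebo was taken. Arm 2, the other half, contributes none of its new placebo-period drugs. The effect is confined to the concomitant-medication classification and the tables built on it; the primary efficacy model and the sample size are untouched. The net bias in the NAL ER versus placebo comparison cannot be estimated from the documents, because the two arms err in opposite directions by unknown amounts. The conclusion assumes literal programming and the planned order and spacing of the periods.

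**What to change.** In the second limb of the placebo rule in SAP Section 4.9, replace first NAL ER intake by first placebo intake, so that the window runs from first to last placebo intake and mirrors the NAL ER rule. Check the program against the corrected text, and record the correction. This costs one word in the SAP and one line of code, and needs no new data.

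While the section is open, state how drugs started and stopped within the washout are tabulated. After the correction they meet neither treatment's rule in either arm, whereas the adverse-event rule in Section 4.12.1.2 assigns events in the first washout to Period 1. This is an additional clarification; the one-word change does not depend on it.
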